6.1.1. Screening Visit

The following assessments and procedures will be performed and recorded on CRFs at the initial Screening Visit:

- Written informed consent from parent or legal guardian and assent from subject, if/when applicable (see above)
- Medical history, including hepatitis B history, hepatitis B treatment history, and family history
- Complete physical examination (excluding breast, anorectal, and urogenital exams), vital signs (temperature, blood pressure, pulse, respiratory rate)
- Body weight and height

- Blood samples for the following will be collected. If all the blood samples cannot be collected in one screening visit, subject may come in at a different visit prior to Baseline to have the remainder of the blood samples collected.
 - Hematology (complete blood count [CBC] with differential and platelet count)
 - Serum chemistry and liver function tests, including albumin, alkaline phosphatase, AST, ALT, total bilirubin (reflex to direct [conjugated] bilirubin if total bilirubin $> 1.5 \times$ ULN), bicarbonate, BUN, calcium, chloride, CPK, creatinine (and calculated creatinine clearance), glucose, LDH, magnesium, phosphorus, potassium, sodium, total iron, uric acid, and amylase (reflex lipase testing if total amylase is $\geq 1.5 \times$ ULN)
 - Prothrombin time (PT), international normalized ratio (INR)
 - Alpha-1 antitrypsin and protease inhibitor (PI) typing
 - Hepatitis B serology (HBeAg and HBsAg; reflex HBeAb and HBsAb if Ag negative)
 - Plasma HBV DNA (PCR method)
 - HIV, HAV, HCV and HDV serology
 - Serum β -HCG test (females of childbearing potential only)
 - α -fetoprotein (AFP)
 - Serum bone biochemical markers, including serum c-telopeptides, osteocalcin, bone-specific alkaline phosphatase, PTH, vitamin D levels (25-hydroxy), 1,25 (dihydroxyvitamin) D levels, and fasting creatinine and fasting phosphate
- Urine samples for:
 - Urinalysis (protein, glucose, blood)
 - Urine bone biochemical markers, including urine bicarbonate, urine n-telopeptide, and spot urine creatinine and phosphate
- Review of AEs and concomitant medications
- Review of all inclusion and exclusion criteria
- Dual energy x-ray absorptiometry (DEXA) scan of spine and whole body (DEXA scan may be performed between Screening and Baseline Visits, but must be performed no later than the Baseline Visit, and prior to receipt of study drugs).

Subjects meeting all of the inclusion criteria and none of the exclusion criteria will return to the clinic within 45 days of the initial Screening Visit for entry into the study. All candidates who meet screening requirements will be randomized and enrolled into the study until the planned enrollment of 100 subjects has been met.

Randomization cannot occur until after the Baseline (pre-treatment) DEXA scan has been performed.

6.1.2. Baseline Assessments

The Baseline Visit should occur within 45 days of the initial Screening Visit. Once eligibility has been confirmed, subjects will be assigned a subject number and treatment arm at the time of randomization. All baseline tests and procedures must be completed prior to the receipt of the first dose of study drugs. Subjects will be dispensed study medication at the Baseline Visit. Study medication should be initiated on-site at the Baseline Visit.

The following assessments and procedures will be performed and recorded on CRFs at the Baseline Visit:

- Review of medical history, hepatitis B history and hepatitis B treatment history and any changes since Screening Visit
- Complete physical examination including Tanner Staging and vital signs
- Body weight and height
- Blood samples for:
 - Hematology (CBC with differential and platelet count)
 - Serum chemistry and liver function tests, including albumin, alkaline phosphatase, AST, ALT, total bilirubin (reflex to direct [conjugated] bilirubin if total bilirubin > 1.5 × ULN), bicarbonate, BUN, calcium, chloride, CPK, creatinine (and calculated creatinine clearance), glucose, LDH, magnesium, phosphorus, potassium, sodium, uric acid, and amylase (reflex lipase testing if total amylase is ≥ 1.5 × ULN)
 - Prothrombin time (PT), international normalized ratio (INR)
 - Hepatitis B serology (HBeAg and HBsAg; reflex HBeAb and HBsAb if Ag negative)
 - Plasma HBV DNA (PCR method)
 - Serum bone biochemical markers, including serum c-telopeptides, osteocalcin, bone-specific alkaline phosphatase, PTH, vitamin D levels (25-hydroxy), 1,25 (dihydroxyvitamin) D levels, and fasting creatinine and fasting phosphate

- Serum β -HCG pregnancy test (females of childbearing potential only)
- Serum for HBV viral genotyping (A–H) and resistance surveillance (sequence analysis of the HBV pol/RT for resistance mutations)
- Plasma for determination of tenofovir concentration
- Serum and plasma for storage (for potential pharmacokinetic and/or virologic assays, including HBsAg and HBeAg quantification and compliance assessment)
- For subjects for whom a separate consent is provided, an appropriate blood sample for biomarker (including pharmacogenomic) analysis will be collected at Baseline (or at the subsequent visits if necessary)
- Urine samples for:
 - Urinalysis (protein, glucose, blood)
 - Urine bone biochemical markers, including urine bicarbonate, urine n-telopeptide, and spot urine creatinine and phosphate
- DEXA scan of spine and whole body (DEXA scan may be performed between Screening and Baseline Visits, but must be performed no later than the Baseline Visit), and prior to receipt of study drugs.
- Review of AEs and concomitant medications
- Study drug dispensing (including multivitamin) and instructions on appropriate dosing and administration

6.2. Treatment Assessments

6.2.1. Week 4, 8, 16, 24, 32, 40 Assessments

The following evaluations will be performed at Weeks 4, 8, 16, 24, 32, and 40, unless otherwise specified. Study visits are to be completed \pm 4 days of the protocol-specified visit date, based on the Baseline Visit. Week 48 assessments are outlined in the following section (Section 6.2.2).

The following assessments and procedures will be performed and recorded on CRFs:

- Symptom-directed physical examination, including vital signs (complete physical examination including Tanner Staging at Week 24 only)
- Body weight and height

- Blood samples for:
 - Hematology (CBC with differential and platelet count)
 - Serum chemistry and liver function tests, including albumin, alkaline phosphatase, AST, ALT, total bilirubin (reflex to direct [conjugated] bilirubin if total bilirubin $> 1.5 \times$ ULN), bicarbonate, BUN, calcium, chloride, CPK, creatinine (and calculated creatinine clearance), glucose, LDH, magnesium, phosphorus, potassium, sodium, uric acid, and amylase (reflex lipase testing if total amylase is $\geq 1.5 \times$ ULN)
 - Hepatitis B serology (HBeAg and HBsAg; reflex HBeAb and HBsAb if Ag negative; Weeks 16 and 32 only)
 - Plasma HBV DNA (PCR method)
 - Plasma for determination of tenofovir concentration
 - Serum and plasma for storage (for potential pharmacokinetic and/or virologic assays, including resistance surveillance, HBsAg and HBeAg quantification and compliance assessment)
- Urine samples for:
 - Urinalysis (protein, glucose, blood)
 - At Week 24 only: urine biochemical markers (refer to Section 6.5. for details)
 - Urine pregnancy test (for females of childbearing potential only; positive urine pregnancy test will be immediately confirmed with a serum pregnancy test)
- At Week 24 only: dual energy x-ray absorptiometry (DEXA) scan of spine and whole body (DEXA scan must be performed ± 10 days from visit)
- Review of AEs and changes in concomitant medications
- Retrieval of study medication and assessment of medication adherence
- Study drug dispensing (including multivitamin) and instructions on appropriate dosing and administration
- At Weeks 4 and 24 only: Provide all subjects with a Subject Dosing Diary Card to complete the diary daily for 10 days prior to the next visit
- At Weeks 8 and 32 only: Collect the Subject Dosing Diary Card completed by the subject daily for 10 days prior to these visits

Subjects who experience Grade 4 ALT while on blinded study medication will be evaluated weekly with serum chemistry and liver function test monitoring. In the event that any subject has sustained Grade 4 ALT for ≥ 16 weeks (i.e., failure to resolve ALT to grade ≤ 3 or baseline), the serial HBV DNA values on study will be provided to the investigator, and the subject can be offered open-label tenofovir DF, after discussion with the Gilead Medical Monitor.

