 - Serum chemistry and liver function tests, including albumin, alkaline phosphatase, AST, ALT, total bilirubin (reflex to direct [conjugated] bilirubin if total bilirubin $> 1.5 \times$ ULN), bicarbonate, BUN, calcium, chloride, CPK, creatinine (and calculated creatinine clearance), glucose, LDH, magnesium, phosphorus, potassium, sodium, uric acid, and amylase (reflex lipase testing if total amylase is $\geq 1.5 \times$ ULN)
 - At Weeks 96, 144, and every 48 weeks during the Extension Phase: Serum bone biochemical markers, including serum c-telopeptides, osteocalcin, bone-specific alkaline phosphatase, PTH, vitamin D levels (25-hydroxy), 1,25 (dihydroxyvitamin) D levels, and fasting creatinine and fasting phosphate
 - Hepatitis B serology (HBeAg and HBsAg; reflex HBeAb and HBsAb if Ag negative) (Weeks 64, 72, 80, 96, and then every 12 weeks until the end of the study including the Extension Phase)
 - Plasma HBV DNA (PCR method)
 - Plasma for determination of tenofovir concentration
 - At Weeks 96 and 144: Serum for resistance surveillance
 - Serum and plasma for storage (for potential pharmacokinetic and/or virologic assays, including resistance surveillance, HBsAg and HBeAg quantification and compliance assessment)
- Urine samples for:
 - Urinalysis (protein, glucose, blood)
 - Urine pregnancy test (for females of childbearing potential only; positive urine pregnancy test will be immediately confirmed with a serum pregnancy test)
 - At Weeks 72, 96, 144, and every 48 weeks during the Extension Phase: Urine bone biomarkers, including urine bicarbonate, urine n-telopeptide, and spot urine creatinine and phosphate

- Weeks 72, 96, 144, and every 48 weeks during the Extension Phase: DEXA scan of spine and whole body (DEXA scan must be performed \pm 10 days from scheduled study visit)
- Review of AEs and concomitant medications
- Retrieval of study medication and assessment of medication adherence
- Study drug dispensing (including multivitamin) and instructions on appropriate dosing and administration
- At Week 56 only: Provide all subjects with a Subject Dosing Diary Card to complete the diary for 10 days prior to the next visit.
- At Week 64 only: Collect the Subject Dosing Diary Card completed by the subject daily for 10 days prior to these visits.

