Subjects who discontinue the study prior to the Week 192 Visit will complete all Week 192 assessments and procedures at an Early Study Drug Discontinuation Visit, to be completed within 72 hours of last dose of study drug. Subsequent off-study therapy, if any, is at the discretion of the subject/physician and will not be provided by Gilead Sciences. Subjects who have received at least one dose of study drug and permanently discontinue study drug will be followed for 24 weeks off treatment or up to initiation of active treatment, whichever occurs first.

The study treatment will end after the each subject reaches Week 192. At Week 192, all active subjects will be offered tenofovir DF through the Extension Phase of the protocol until it becomes commercially available in that country for treatment of chronic HBV in patients of their age and weight. If the subject is off treatment following Week 192, the treatment-free follow-up period is required (Section 6.3.1).

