6.3.2. Assessments for Premature Discontinuation from the Study (Early Study Drug Discontinuation Visit)

Subjects who permanently discontinue study drug prior to the end of the study (Week 192) will be asked to return to the clinic within 72 hours of stopping study drug for an Early Study Drug Discontinuation Visit. Subjects who discontinue the study prior to the Week 192 Visit will complete all Early Discontinuation assessments and procedures (see Section 6.3.1 above). Subjects who have received at least one dose of study drug and permanently discontinue study drug will be followed with visits every 4 weeks for 24 weeks off treatment or up to initiation of active treatment, whichever occurs first. Subsequent off-study therapy, if any, is at the discretion of the subject/physician and will not be provided by Gilead Sciences.

Subjects experiencing post-treatment exacerbation of hepatitis during the 24-week post-treatment period should be followed weekly until their ALT levels return to Grade 2 or baseline, as described in the Toxicity Management section of the protocol (Section 7.6).

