6.5. Bone Biochemical Markers

Laboratory samples will be taken at screening, baseline and at Weeks 24, 48, 72, 96, 144, 192, every 48 weeks during the Extension Phase, and the Early Study Drug Discontinuation/End of Treatment Visit, if applicable, for measuring bone biochemical markers. In addition, bone biochemical markers will be measured at the time of switch in subjects switching from placebo to tenofovir DF, unless the previous measurements were ≤ 12 weeks prior.

Analyses will include measurements of urine bicarbonate and n-telopeptide; measurements of serum c-telopeptides, osteocalcin, bone-specific alkaline phosphatase, PTH, and vitamin D levels (25-hydroxy) and 1,25 (dihydroxyvitamin) D levels; and fasting serum creatinine/phosphate and urine creatinine (spot)/phosphate for measurement of the renal phosphate threshold (TmP/GFR).

The mean of the Screening and Baseline Visit values will constitute the study baseline value to which all subsequent values will be compared. Bone biochemical markers can be affected by the time of day (diurnal variation) and food. Therefore, subjects will be asked to report for each of these visits in the morning in a fasted state or, if fasting is not feasible, at the same time (± 2 hours from the Baseline Visit draw time) at each subsequent visit. All samples will be sent to a central laboratory in accordance with the laboratory procedure manual. Bone biochemical marker results will not be provided to the study sites.

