7.3.2. Bone Biochemical Markers

Baseline, postbaseline, and change from baseline in bone biochemical markers, including urine bicarbonate, urine n-telopeptide, serum c-telopeptides, osteocalcin, bone specific alkaline phosphatase, PTH, vitamin D levels (25-hydroxy) and 1, 25 (dihydroxyvitamin) D levels, fasting serum creatinine and phosphate, spot urine creatinine and phosphate, and renal phosphate threshold (TmP/GFR) will be summarized by treatment group and visit using the Safety Analysis Set. The change from baseline in bone biochemical markers will be compared using the Wilcoxon rank-sum test up to Week 48. Supportive listings for bone biochemical marker measurements will also be provided. For fasting serum and fasting creatinine, only measurements taken when subject was confirmed to be fasting will be reported.

To calculate TmP/GFR, the following formula will be used based on serum creatinine and only for subjects confirmed to be fasting {Barth 2000}:

$$TmP/GFR = TRP \times SPO_4 \quad \text{if } TRP \leq 0.86$$
$$TmP/GFR = 0.3 \times TRP / [1 - (0.8 \times TRP)] \times SPO_4 \quad \text{if } TRP > 0.86$$

where TRP (tubular reabsorption of phosphate) is calculated by:

$$TRP = 1 - \frac{UPO_4}{SPO_4} \times \frac{SCr}{UCr}$$

where SCr is serum creatinine concentration (mg/dL), UPO₄ is urine phosphate concentration (mg/dL), SPO₄ is serum phosphate concentration, and UCr is urine creatinine concentration (mg/dL).

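### The visit lists omit serum bone markers at Weeks 24 and 72, and Section 6.3.2 points the early-discontinuation visit to a list without DEXA or bone markers, in conflict with Sections 6.5 and 6.2.4 and Appendix 2

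*Protocol*

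**What the plan says.** **Marker schedule.** Protocol Section 6.5 states: "Laboratory samples will be taken at screening, baseline and at Weeks 24, 48, 72, 96, 144, 192". Its panel covers urine markers and "measurements of serum c-telopeptides, osteocalcin, bone-specific alkaline phosphatase, PTH, and vitamin D levels (25-hydroxy", then 1,25-dihydroxyvitamin D, and fasting serum with spot urine creatinine and phosphate for TmP/GFR. The Appendix 2 rows mark Weeks 24 and 72, footnote n repeats those weeks, and Appendix 3 defines the panel as serum plus urine. The synopsis and Section 3 give the same 24-weekly rhythm through Week 96. SAP Table 3-3 sets Week 24 and Week 72 windows for the named serum analytes.

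**Visit lists.** In Section 6.2.1 the only marker entry stands under urine samples: "At Week 24 only: urine biochemical markers (refer to Section 6.5. for details". Section 6.2.3 gives the serum line as "At Weeks 96, 144, and every 48 weeks during the Extension Phase: Serum bone biochemical markers" and the urine line as "At Weeks 72, 96, 144, and every 48 weeks during the Extension Phase: Urine bone biomarkers".

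**Early discontinuation.** Section 6.2.4 says that subjects who stop before Week 192 "will complete all Week 192 assessments and procedures at an Early Study Drug Discontinuation Visit". DEXA and markers are required there if the last were more than 12 weeks earlier (visit before Week 96) or more than 24 weeks earlier (visit after Week 96). Appendix 2, in its early-discontinuation column and footnote r, agrees. Section 6.3.2 says that they "will complete all Early Discontinuation assessments and procedures (see Section 6.3.1 above", and the closing text of Section 6.2.2 sends children who stop before Week 48 to Section 6.3.

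**Use of the data.** SAP Section 7.3.2: "The change from baseline in bone biochemical markers will be compared using the Wilcoxon rank-sum test up to Week 48".

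**The concern.** The visit lists are working instructions for sites. At Baseline, Week 48 and Week 192 they spell out the serum panel, so its absence at Weeks 24 and 72 can be read as intended. Section 6 says that procedures are given both in Appendix 2 and in the text, and does not say which governs if they differ.

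Week 24 is one of only two post-baseline marker visits in the 48-week placebo-controlled comparison, and the SAP tests the arms against each other at visits up to Week 48. For placebo children who switch at Week 48, Week 72 is the first scheduled marker visit on tenofovir DF.

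The early-discontinuation conflict matters because any loss would be selective: it would fall on children who stop, including those who stop for toxicity. The protocol background reports reduced bone accrual and renal discontinuations consistent with proximal tubulopathy in children, and Section 8.12 asks the DMC to review bone and renal data.

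**Working it through.** The plan gives no figure to reproduce; the check sets the schedules side by side.

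**1. Serum bone markers, post-baseline through Week 192**

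| Week | Section 6.5 / Appendix 2 | Visit list, serum | Visit list, urine |
|---|---|---|---|
| 24 | yes | no (6.2.1) | yes |
| 48 | yes | yes (6.2.2) | yes |
| 72 | yes | no (6.2.3) | yes |
| 96 | yes | yes (6.2.3) | yes |
| 144 | yes | yes (6.2.3) | yes |
| 192 | yes | yes (6.2.4) | yes |

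Serum: 6 scheduled, 4 listed, 6 − 4 = 2 missing. Urine: 6 of 6 listed. In the 48-week blinded comparison (Weeks 24 and 48), 1 of 2 serum panels is missing from the lists.

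**2. Analytes exposed.** Where the lists spell it out, the serum panel has 8 items: c-telopeptides, osteocalcin, bone-specific alkaline phosphatase, PTH, 25-hydroxyvitamin D, 1,25-dihydroxyvitamin D, fasting creatinine and fasting phosphate. Routine chemistry at Weeks 24 and 72 already includes creatinine and phosphorus, without a fasting requirement. So 8 − 2 = 6 analytes would be absent. SAP Section 7.3.2 computes TmP/GFR from serum and urine creatinine and phosphate, only in subjects confirmed to be fasting. It stays derivable for a child who came fasted with a urine sample, and is unusable otherwise.

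**3. Placebo children switching at Week 48.** The first scheduled serum panel on drug is at 72 − 48 = 24 weeks of exposure. If Week 72 is missed, it is at 96 − 48 = 48 weeks.

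**4. The list reached through Section 6.3.2.** Section 6.3.1 is the 4-weekly off-treatment list. It has no DEXA, bone markers, hematology, urinalysis or dedicated resistance sample, and serology only at Follow-Up Week 24. It does keep chemistry, HBV DNA and stored serum.

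**5. When a DEXA is owed at early discontinuation.** Assume scans on nominal dates and a baseline scan at Day 1.
- Before Week 96, scans fall at Weeks 0, 24, 48, 72 and 96. A scan is owed in the last 12 weeks of each 24-week interval: 4 × 12 = 48 of 96 weeks (24 of 48 in the blinded phase).
- After Week 96, scans fall at Weeks 96, 144 and 192. A scan is owed in the last 24 weeks of each 48-week interval: 2 × 24 = 48 of 96 weeks.

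A scan is therefore owed over about half the calendar, 96 of 192 weeks.

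**6. What an owed scan contributes.** Take a child who stops at Week 16. The baseline scan is 16 weeks old, more than 12, so a scan is owed. Day 16 × 7 = 112 lies in the SAP Week 24 window (Days 2 to 251). Done within 3 days of the last dose, it counts as on-treatment (SAP Section 3.8.2). It would be that child's only post-baseline BMD value for the comparison of decreases of at least 4% in SAP Section 7.3.1.

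**The case against.** The strongest reply is that the schedule is fixed correctly and repeatedly elsewhere, so only a site that ignores all of it would go wrong. The Week 24 line itself refers to Section 6.5, which names the serum panel. Section 6.2.4 carries early discontinuation in its title and gives the list. Section 6.3.2 asks for the early-discontinuation assessments, so its reference to Section 6.3.1 looks like a wrong section number. DEXA is listed at Weeks 24, 48 and 72, so the lumbar-spine BMD endpoints at scheduled visits do not depend on this. Serum markers are not listed endpoints; protocol Section 8.9.4 only summarises them, and it is the SAP that adds a test. Placebo children who switch at Week 72 are covered by the switch rule in Sections 6.4 and 6.5, since their Week 48 panel is 24 weeks old, beyond the 12-week limit. Enrolment stopped at 90 randomized (SAP Section 1.3), so a Week 24 correction may come too late.

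Most of this stands, and it limits the consequence. It does not remove the inconsistency. The Week 72 serum line has no pointer to Section 6.5, Section 6.3.2 and the end of Section 6.2.2 still conflict with Section 6.2.4, and no rule of precedence is given.

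A reader might infer that Week 24 and Week 72 serum data and TmP/GFR were lost, or that every child who stops early loses a last DEXA. The documents support neither. They do not report what was collected, routine chemistry keeps creatinine and phosphorus, and the early-discontinuation scan is conditional.

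**Conclusion.** The concern holds as an internal inconsistency, not as a fault in the design. A site working from the lists alone could miss 2 of 6 post-baseline serum panels, including 1 of 2 in the blinded comparison, with six analytes absent and TmP/GFR at risk. A site following Section 6.3.2 would omit DEXA and bone markers at early discontinuation in those cases where the 12- or 24-week rule calls for them.

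The size of any actual loss cannot be stated. It depends on how many sites worked from the lists and how many children stopped when a scan was owed, and the documents give neither. The half-of-calendar figure also assumes scans on nominal dates. Urine markers, the Week 48 panel, and scheduled BMD data at Weeks 24, 48 and 72 are unaffected. It should be corrected because the passages are operative instructions and feed planned SAP analyses.

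**What to change.** - Reconcile the Week 24 blood list in Section 6.2.1 and the Week 72 serum entry in Section 6.2.3 with Section 6.5 and Appendix 2, including the fasting condition.
- Reconcile the cross-references in Section 6.3.2 and at the end of Section 6.2.2 with Section 6.2.4 and footnote r of Appendix 2.
- Send sites a clarification for the remaining visits.
- Check whether the Week 24, Week 72 and early-discontinuation samples and scans were collected. Report the number available by arm with the marker and BMD analyses, so that any gap is visible.

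The cost is two list entries, two cross-references, a site memo and a data check. No procedure is added beyond those Appendix 2 already schedules. The wording change may come too late for Week 24 visits; for those, the data check is the useful part.
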